5.4. SAFETY ANALYSIS SET

The Safety Analysis Set will include all randomised participants who received at least one dose of study drug. Participants in this set will be analysed based on the actual treatment that they received. All safety summaries will be based on the Safety Analysis Set.

5.5. PHARMACOKINETIC ANALYSIS SET

The pharmacokinetic (PK) Analysis Set will include all participants included in the safety set who have sufficient concentrations to allow for the calculation of at least one PK parameter. Participants who experience any adverse events or have protocol deviations that could affect the PK profiles may be excluded from the PK analysis set at the pharmacokineticist's discretion. Participants in this set will be analysed based on the actual treatment that they received. All PK analyses will be based on the PK Analysis Set.

6. GENERAL CONSIDERATIONS

Listings will be presented using All Participants Enrolled Set for those participants with data available.

6.1. SUMMARY STATISTICS

For categorical variables, the population size (N for population group totals and n for available data for each treatment group) and the percentage (of available data) for each class of the variable will be presented. Continuous variables will be summarized using descriptive statistics, including number of participants (n), mean, standard deviation (SD), median, minimum, and maximum values. The coefficient of variation (CV%), geometric mean and geometric CV% will be presented for the PK tables.

95% Confidence Intervals will be reported where appropriate. If not mentioned otherwise, all statistical tests will be performed with a type I two-sided error rate of 5%.

6.2. TREATMENT SUMMARIZATION

Results will be presented for each treatment group, for the pooled FT011 group and overall.

6.3. PRECISION

All continuous demographic and safety variables (i.e., clinical laboratory values, vital signs, body weight and ECG intervals), including derivations thereof, will be reported to the same precision as the source data.

For the reporting of descriptive statistics, the mean and median will be presented to one digit more than the source data. The standard deviation will be presented to two digits more than the source data. The minimum and maximum will be presented to the same precision as the source data.

Document: \$506df00529e1\$BDE32479744D47F0B3BAA4285D5BE091.docx

Author: ████████████████████

Version Number: Final v1.1

Version Date: 16Nov2022

Template No.: CS_TP_BS016 Revision 6

Reference: CS_WI_BS005

Effective Date: 02Dec2019

PK data (concentration-time and PK parameters) will be presented to three significant digits.

Percentages will be reported to one decimal point.

6.4. REFERENCE START DATE AND STUDY DAY

Study Day will be calculated from the date of first study drug administration and will be used to show start/stop day of assessments and events.

- If the date of the event is on or after the date of first study drug administration then:

Study Day = (date of event – date of first study drug administration) + 1

- If the date of the event is prior to the date of first study drug administration then:

Study Day = (date of event – date of first study drug administration)

There will be no Study Day 0.

In the situation where the event date is partial or missing, study day and any corresponding durations will appear partial or missing in the listings.

6.5. BASELINE

In general, baseline is defined as the last available, valid, non-missing measurement taken prior to first study drug administration (including unscheduled assessments). In the case where the last non-missing measurement and the reference start date coincide, that measurement will be considered pre-baseline, but adverse events (AEs) and medications commencing on the reference start date will be considered post-baseline.

6.6. ON-TREATMENT

A participant will be identified as on-treatment if the last available, valid, non-missing measurement taken prior to cut-off date indicates the participant is receiving a study drug.

6.7. RETESTS, UNSCHEDULED VISITS AND EARLY TERMINATION DATA

Unscheduled measurements will not be included in summaries at each protocol specified time point. However, unscheduled assessments will be taken into consideration in the calculation of baseline values.

Early termination results will be recorded as such and included with the end-of-study summaries.

In the case of a retest of a scheduled assessment, the retested measurement for that scheduled time (i.e., the original assessment) will be used for summaries unless flagged as invalid.

In the case of duplicate tests with the same sample date/time (in particular, where a lab sample is analysed at two separate labs), for quantitative results, the mean of the values will be used in the

Document: \$506df00529e1\$BDE32479744D47F0B3BAA4285D5BE091.docx

Author: [REDACTED]

Version Number: Final v1.1

Version Date: 16Nov2022

Template No.: CS_TP_BS016 Revision 6

Reference: CS_WI_BS005

Effective Date: 02Dec2019

Copyright © 2009, 2010, 2012, 2016, 2018, 2019 IQVIA. All rights reserved. The contents of this document are confidential and proprietary to IQVIA Holdings Inc. and its subsidiaries. Unauthorized use, disclosure or reproduction is strictly prohibited.

summary tables and for qualitative results, the most abnormal of the values will be used in the summary tables. The listings will present the duplicate values.

Data from unscheduled visits/time points will be included in the figures (where appropriate) and data listings.

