#### **5.4.8 Stopping Rules / Discontinuation Criteria**

##### **5.4.8.1 Individual Participant Stopping Rules**

Safety laboratory testing will be performed by a study central laboratory.

If ALT or AST > 3 x ULN, the participant must have repeat testing conducted within 48 to 72 hours to confirm the values.

If the elevation is confirmed as >3 x ULN, close observation that includes elicitation of a detailed history and performance of diagnostic laboratory studies to exclude other causes of acute liver injury must be conducted. In addition, participants must have their liver chemistry (ALT, AST, ALP, international normalised ratio (INR) and total bilirubin) retested at least once weekly until levels normalise or return to baseline.

In the event of confirmed laboratory results (i.e. confirmed on retest within 48 to 72 hours) meeting any of following criteria, IMP will be stopped permanently for that participant:

- ALT or AST >8 x ULN
- ALT or AST >5 x ULN for more than 2 weeks
- ALT or AST >3 x ULN and either bilirubin >2 x ULN or INR >1.5
- ALT or AST >3 x ULN with the appearance of fatigue, nausea, vomiting, right upper quadrant pain or tenderness, fever, rash, and/or eosinophilia (>5%).

If serum creatinine is  $\geq$  Grade 3 (based on the Common Terminology Criteria for Adverse Events (CTCAE)), IMP will be stopped for that participant and they will be monitored until values return to Grade 1. IMP may then be restarted but stopped permanently if there is a recurrence of serum creatinine levels  $\geq$  Grade 3.

All participants should attend the follow up visit 4 weeks after their last dose of IMP.

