### **12.2 General Methodology**

Results will be presented by treatment group, for the pooled FT011 group and overall.

In general, data will be summarised using descriptive statistics (number of observations, mean, median, standard deviation [SD], minimum and maximum) or frequency counts and percentages, as appropriate to the type of data. The coefficient of variation (CV), geometric mean and geometric CV will also be presented for the PK tables.

Confidence intervals will be reported where appropriate. If not mentioned otherwise, all statistical tests will be performed with a type I two-sided error rate of 5%.

Baseline will be defined as the last available, valid, non-missing assessment prior to the first study drug administration.

Only data from protocol scheduled visits/time points will be included in the summary tables. Data from unscheduled visits/time points will be included in the figures (where appropriate) and data listings.

Medical history and adverse event terms will be coded by Medical Dictionary for Regulatory Activities (MedDRA) codes and prior and concomitant medications by the World Health Organisation Drug Dictionary (WHO-DD) Anatomical Therapeutic Chemical (ATC) classification codes. The specific dictionary versions will be documented in the SAP and in the outputs.

The software (and version) used to perform the statistical and PK analyses will be documented in the SAP.

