15.2. LABORATORY EVALUATIONS

Central safety laboratory results will be included in the reporting of this study for haematology, biochemistry, coagulation, urinalysis, and serum pregnancy testing. No lab data imputation will be performed. Incomplete data may be excluded from some analyses. In cases where an analysis depends on identifying an abnormal value, only values which are non-missing and which can be clearly identified programmatically as abnormal will be counted.

Presentations will use SI Units, as provided by the laboratory.

Quantitative laboratory measurements reported as "<X", i.e. below the lower limit of quantification, or "> X", i.e. above the upper limit of quantification, will be converted to X for the purpose of quantitative summaries, but will be presented as recorded, i.e. as "<X" or "> X" in the listings.

Laboratory data will be summarized using descriptive statistics. Clinical laboratory data collected during study conduct, which were not required per protocol, such as for special testing to evaluate an AE, will be listed and not summarized.

All laboratory data is summarised and listed for all visits where data is collected. The following summaries are provided for laboratory data:

Actual values and change from baseline will be summarized using descriptive statistics at each protocol specified time point, by treatment group.

- Shift from baseline will be summarized at each post-baseline protocol scheduled time by treatment group, using frequency tabulations.

Document: \$506df00529e1\$BDE32479744D47F0B3BAA4285D5BE091.docx

Author: [REDACTED]

Version Number: Final v1.1

Version Date: 16Nov2022

Template No.: CS_TP_BS016 Revision 6

Reference: CS_WI_BS005

Effective Date: 02Dec2019

- Separate listings will be produced for all participants with at least one out-of-range or abnormal clinical laboratory result. In these listings, the full time point profile will be presented for the parameter with the out-of-range or abnormal value.

A list of laboratory assessments to be included in the outputs is included below:

- Haematology: Haemoglobin, haematocrit, red blood cell count, red cell distribution width, mean corpuscular volume, mean corpuscular haemoglobin, mean corpuscular haemoglobin concentration, white blood cell count, neutrophils, lymphocytes, monocytes, eosinophils, basophils, and platelet count

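### The SAP retest rule names two different values and unscheduled tests stay out of the by-visit summaries, so a transient liver elevation, or the peak and duration of a confirmed one, can be missing from the by-arm laboratory tables

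*SAP*

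**What the plan says.** Four sets of provisions meet on this point.

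- **Retest rule.** When a scheduled assessment is retested, SAP 6.7 says "the retested measurement for that scheduled time (i.e., the original assessment) will be used for summaries unless flagged as invalid".
- **Unscheduled results.** SAP 6.7: "Unscheduled measurements will not be included in summaries at each protocol specified time point". Protocol 12.2 agrees: "Only data from protocol scheduled visits/time points will be included in the summary tables". They appear elsewhere: "Data from unscheduled visits/time points will be included in the figures (where appropriate) and data listings" (SAP 6.7). SAP 6.8 applies no visit windowing, so a later draw is not reassigned to a visit.
- **Why repeats arise.** Under Protocol 5.4.8.1, if ALT or AST is above 3 x ULN, "the participant must have repeat testing conducted within 48 to 72 hours to confirm the values". Once the rise is confirmed, liver chemistry must be "retested at least once weekly until levels normalise or return to baseline". Scheduled post-baseline visits are at Weeks 4, 8, 12 and 16 (Protocol Table 1).
- **Laboratory tables.** SAP 15.2 plans two by-arm summaries: "Actual values and change from baseline will be summarized using descriptive statistics at each protocol specified time point, by treatment group", and "Shift from baseline will be summarized at each post-baseline protocol scheduled time by treatment group". The descriptive statistics include the minimum and maximum (SAP 6.1). The reference-range categories are Low, Normal and High only.

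SAP 15.2 also plans a listing that gives the full time-point profile of any parameter with an out-of-range or abnormal result. SAP Appendix 3 includes a DSMB table of clinically significant laboratory values.

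**The concern.** The retest sentence equates two values that differ by construction. Two programmers could each follow it and produce different tables, and the closing condition about invalid results could attach to either value. The 48 to 72 hour repeat might also be classed as an unscheduled measurement and be excluded on that ground.

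The participants affected are those with a liver signal, because the protocol forces repeats only for them. Safety and tolerability compared with placebo is the first secondary objective. The by-visit and shift tables are the only by-arm laboratory summaries that SAP 15.2 describes for the final analysis. Protocol 5.4.3 (criterion 11) excludes anyone with ALT, AST or bilirubin above ULN at Screening or Baseline, so every eligible participant starts as Normal for these tests. A shift to High then looks the same at 1.1 x ULN as at 8 x ULN. No described table uses the thresholds in Protocol 5.4.8.1, and none gives the worst post-baseline value.

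**Working it through.** The plan states no figure here to reproduce. The check follows assumed ALT sequences through the two readings of SAP 6.7.

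**Inputs from the documents:** 10 participants per arm (SAP 3.1); High means above ULN (SAP 15.2); repeat at 48 to 72 hours, then at least weekly (Protocol 5.4.8.1); unscheduled values excluded from by-visit summaries (SAP 6.7, Protocol 12.2).

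**Assumed:** the ALT sequences below, in multiples of ULN, with the other nine participants in the arm at 0.6 x ULN.

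**Formula:** visit mean = (9 x 0.6 + v)/10 = (5.4 + v)/10, where v is the value that enters the table.

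| Case | Original used | Retest used | True peak |
|---|---|---|---|
| 1. Transient at a scheduled visit: 3.5, repeat 0.9 | mean 0.89, max 3.5, High 1/10 | mean 0.63, max 0.9, High 0/10 | 3.5 |
| 2. Confirmed at a scheduled visit: 3.5, repeat 4.0 | mean 0.89, max 3.5, High 1/10 | mean 0.94, max 4.0, High 1/10 | 4.0 |
| 3. As case 2, then weekly 8.5, 5.5, 2.0; normal by next visit | v = 3.5, High | v = 4.0, High | 8.5 |
| 4. Scheduled 0.8; unscheduled 6.0, 6.2, 2.0; normal by next visit | v = 0.8, Normal | v = 0.8, Normal | 6.2 |

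Arithmetic: (5.4 + 3.5)/10 = 0.89; (5.4 + 0.9)/10 = 0.63; (5.4 + 4.0)/10 = 0.94.

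What each case shows:

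1. The reading decides whether a transient rise appears at all.
2. A confirmed rise found at a scheduled visit is High under both readings.
3. The rise is visible as High, but the tables show 3.5 or 4.0 against a true peak of 8.5. They do not show how long it lasted between visits four weeks apart.
4. The rise is absent under both readings. The exclusion of unscheduled results causes this, not the retest sentence.

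A repeat that falls but stays above ULN belongs with case 2 for the High count. With an assumed ULN of 40 U/L and nine others at 25 U/L, 200 followed by 110 is 5 then 2.75 x ULN, which is High either way. Only the mean moves: (200 + 225)/10 = 42.5 or (110 + 225)/10 = 33.5.

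**Bilirubin.** Protocol 5.4.8.1 puts total bilirubin in the weekly retests, but its stopping criterion says only bilirubin. The routine chemistry panel (Protocol 8.2) and the SAP 15.2 output list name direct bilirubin only. On that text, total bilirubin may exist only in draws that the by-visit tables exclude. The passages need to be reconciled.

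**With a maximum post-baseline table**, the four cases would be reported as 3.5 (above 3), 4.0 (above 3), 8.5 (above 8) and 6.2 (above 5) x ULN, whichever reading of SAP 6.7 is used.

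**The case against.** The best defence is grammatical. The phrase can mean the measurement that was retested, with the bracket explaining that this is the original. The neighbouring rules fit that reading: unscheduled values stay out, no windowing is applied, and a draw two or three days later is not a protocol time point. This is plausible, and the fix adopts it. But the text also supports the other reading, and choosing this one does nothing for cases 3 and 4.

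A second defence is that SAP 15.2 opens its summaries with a general statement that laboratory data are summarised for all visits where they are collected. The specific summaries that follow are limited to protocol time points, and SAP 6.7 and Protocol 12.2 say the same.

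A third is that nothing is hidden. Listings hold every value and the abnormal-result listing gives the full profile. With about ten per arm and no statistical comparison of safety outcomes (SAP 15), listings are workable. An elevation reported as an adverse event also reaches the TEAE tables. This stands as to visibility. However, a listing is not a by-arm summary, and Protocol 10.3 generally makes a laboratory finding an adverse event only with a diagnosis, signs or symptoms, discontinuation, seriousness or investigator-judged significance.

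A reader might infer two stronger conclusions that the documents do not support.

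- **That a confirmed elevation can vanish from every laboratory table.** Confirmed means that the repeat is also above 3 x ULN, so a rise found at a scheduled visit is High under either reading. The DSMB table in Appendix 3 is not stated to be limited to scheduled visits. The table templates that SAP 8 refers to are not in the documents.
- **That stopping decisions are compromised.** The individual and study rules in Protocol 5.4.8 act on results as they arrive. They do not depend on the final tables.

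**Conclusion.** The point holds as a reporting defect in the SAP and should be corrected. The retest rule is ambiguous as written. If the retest replaces the original, a transient ALT or AST elevation that normalises on the repeat drops out of the by-visit and shift tables (High 1/10 becomes 0/10 in case 1). Under either reading, the between-visit peak and duration of a confirmed elevation, and any elevation first seen at an unscheduled draw and resolved by the next visit, are missing from the SAP 15.2 by-arm tables. They remain in the listings, and in the TEAE tables only if reported as adverse events.

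The sizes rest on assumed ALT values, because the documents give no expected rate or pattern of elevations. The conclusion about missing tables rests on SAP 15.2 as described, without sight of the templates.

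**What to change.** 1. Reword the SAP 6.7 sentence: by-visit summaries and shift tables use the original valid scheduled value, and retests are listed. State what is used if the original is flagged invalid.
2. Add one by-arm table to SAP 15.2 of each participant's maximum post-baseline value, taken over scheduled, unscheduled and repeat results, in the categories of Protocol 5.4.8.1: ALT and AST above 3, 5 and 8 x ULN; bilirubin above 2 x ULN; INR above 1.5; creatinine Grade 3 or above. Name the bilirubin analyte, after the protocol and SAP passages on total and direct bilirubin have been reconciled.
3. Title it as a table of peak values. It does not show whether a stopping rule was met, because those rules also involve confirmation, persistence and combinations. Duration would still be read from the full-profile listing.

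The cost is one SAP sentence and one extra table from data already collected. No clinical rule, visit or sample changes.

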6.8. WINDOWING CONVENTIONS

No visit windowing will be performed for this study.

6.9. STATISTICAL TESTS

Where indicated, two-sided confidence intervals will be assessed at the 5% significance and two-sided p-value will be reported.

6.10. COMMON CALCULATIONS

For continuous measurements:

Actual change from baseline will be calculated as:

- Test Value at Visit X (after baseline) – Baseline Value

6.11. SOFTWARE VERSION

All derivations, statistical analyses, summaries and listings will be generated using SAS version 9.4 or higher (SAS Institute, Inc., Cary, North Carolina). PK Parameters will be calculated using WinNonlin version 8.3 or higher (Certara, LP Princeton, New Jersey, USA).

7. STATISTICAL CONSIDERATIONS

7.1. ADJUSTMENTS FOR COVARIATES AND FACTORS TO BE INCLUDED IN ANALYSES

The baseline values will be included as a covariate, treatment group will be included as a fixed effect, and the interaction effect between study visit and treatment group, and participant will be included as random effects in the mixed models for efficacy analysis.

No additional adjustments for covariates will be made.

Document: \$506df00529e1\$BDE32479744D47F0B3BAA4285D5BE091.docx

Author: ██████████

Version Number:

Final v1.1

Version Date:

16Nov2022

Template No.: CS_TP_BS016 Revision 6

Reference: CS_WI_BS005

Effective Date: 02Dec2019

Copyright © 2009, 2010, 2012, 2016, 2018, 2019 IQVIA. All rights reserved. The contents of this document are confidential and proprietary to IQVIA Holdings Inc. and its subsidiaries. Unauthorized use, disclosure or reproduction is strictly prohibited.

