#### **6.2 Screening Visit (Day -28 to Day -1)**

The purpose of the Screening visit is to confirm participant eligibility against inclusion and exclusion criteria.

In this study, participant eligibility must be determined within the 28 days prior to Day 1. Screening assessments may be conducted on different days during the Screening period if required due to timing, or participant availability.

Potential participants will attend the in-clinic screening. Once informed consent has been obtained, the following visit assessments and procedures will be performed:

- Review eligibility criteria.
- Record participant demographic data.

- Review and record medical history and current conditions, including SSc-specific signs and symptoms
- Investigator assessment of the mRSS (see Section 8.3)
- Physical examination, including weight and height (see Section 8.2).
- Measurement of vital signs including blood pressure, heart rate, respiratory rate, and temperature (see Section 8.2).
- Spirometry assessment of FVC and forced expiratory volume in 1 second (FEV1) (see Section 8.3)
- 12-lead ECG (see Section 8.2).
- Safety laboratory tests including haematology, biochemistry, coagulation, and urinalysis, and serum pregnancy test for WOCBP (see Section 8.2).
- Review and record current and past medications.

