## **6.3 Treatment Period**

### **6.3.1 Day 1 (Baseline)**

Participants who meet all the inclusion and none of the exclusion criteria will be scheduled to return to the site for their Day 1 visit. This visit may be conducted over two consecutive days, as long as the dosing and PK samples are collected on the second day. The dosing day visit should be conducted in the morning, and the participant should be fasted (except for water, which is allowed) for approximately 8 hours prior to the visit.

At this visit the following will be performed:

- Confirm participant continues to meet eligibility criteria.
- Patient Global Assessment of disease severity (see Section 8.3).
- Record any new medical events since Screening, including SSc-specific signs and symptoms.
- Investigator assessment of the mRSS (see Section 8.3).
- Completion of the Scleroderma Health Assessment Questionnaire- Disability Index (SHAQ-DI) (see Section 8.3).
- Completion of the Scleroderma Clinical Trial Consortium Damage Index (SCTC-DI) (see Section 8.3).
- Completion of the 5-D Itch Scale (see Section 8.3).
- Symptom-directed physical examination (see Section 8.2).

- Weight.
- Measurement of vital signs pre-dose including blood pressure, heart rate, respiratory rate, and temperature (see Section 8.2).
- Spirometry assessment of FVC and FEV1 (see Section 8.3).
- Physician Global Assessment of disease severity (see Section 8.3).
- 12-lead ECG (see Section 8.2).
- Blood samples:
  - Pre-dose collection of blood samples for immune cell activation markers (see Section 8.4).
  - Pre-dose PK sample collected (see Section 8.1).
  - Pre-dose blood samples collected for cytokine and chemokine measurements (see Section 8.4).
  - Safety laboratory tests including haematology, biochemistry, coagulation, and urinalysis, and serum pregnancy test for WOCBP (see Section 8.2).
- Collect 2 x 3mm punch biopsy skin samples (see Section 8.4). For operational reasons, biopsies may be collected during the screening period once participants have been confirmed as eligible, as long as they are collected pre-dose.
- Review and record concomitant medications.

Eligible participants will be randomised, dispensed IMP, and will take their first dose of IMP at the study site, with the time of administration recorded.

- Participants will remain on site for PK blood samples to be collected at 1, 2, 3, 4, 5, 6, 7 and 8 hours post dose (see Section 8.1).

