14.2.1.10 ANALYSIS OF EFFICACY VARIABLES

The observed values and change from baseline values for mRSS, percent predicted FVC, HAQ-DI, patient global assessment score, and physician global assessment score, and SCTC-DI score will be listed for each participant at each protocol specified visit and will be summarised using descriptive statistics over time by treatment group and for all participants.

Actual and change from baseline values will be presented graphically by treatment group using a jitter plot and overlaid box-whisker plot (median, 25th and 75th percentiles) over time.

For mRSS, HAQ-DI, SCTC-DI and 5-D Itch Scale the individual item responses will also be summarised and listed for each participant.

The 5-D itch scale at baseline and at Week 12 will be listed for each participant and will be summarised using descriptive statistics. The change from baseline to Week 12 will also be summarised.

Even though no formal hypothesis testing is planned for this study, exploratory analyses may be performed to assess the treatment effect of FT011 on the efficacy outcomes if data indicates trend and model assumptions hold.

For mRSS, percent predicted FVC, HAQ-DI, patient global assessment score, and physician global assessment score, the change from baseline values will be compared between the FT011 and placebo groups using a mixed model for repeated measures with the baseline value as a covariate, treatment group as fixed effect, the interaction effect between study visit and treatment group, and participant as random effect using an unstructured covariance structure. Parameter estimates will be calculated using restricted maximum likelihood methods (REML), and the Kenward-Rogers method for determining the degrees of freedom. This method will assume that any missing data is Missing at Random (MAR). Example SAS code for the mixed model (using SAS Proc Mixed) is:

Document: \$506df00529e1\$BDE32479744D47F0B3BAA4285D5BE091.docx

Author: ████████████████████

Version Number: Final v1.1

Version Date: 16Nov2022

Template No.: CS_TP_BS016 Revision 6

Reference: CS_WI_BS005

Effective Date: 02Dec2019

```
PROC MIXED data=libname.ADXX REML;  
CLASS TRT01P VISIT SUBJID;  
MODEL AVAL = TRT01P|VISIT BASELINE / DDFM = KENWARDROGER;  
RANDOM VISIT / SUBJECT = SUBJID TYPE = UN;  
LSMEANS TRT01P|VISIT / PDIFF = CONTROL('PLACEBO') CL ;  
RUN;
```

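### Screening mRSS and FVC are collected but left out of the efficacy model; adding them as a second covariate would modestly narrow the FVC intervals and might narrow those for mRSS

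*SAP*

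**What the plan says.** Protocol 6.2 lists for Screening "Investigator assessment of the mRSS (see Section 8.3") and "Spirometry assessment of FVC and forced expiratory volume in 1 second (FEV1) (see Section 8.3"). Protocol 6.3.1 repeats both on Day 1, including "Spirometry assessment of FVC and FEV1 (see Section 8.3"), and Table 1 agrees. Screening values are needed for eligibility (mRSS 15 to 40, FVC at least 50% of predicted; Protocol 5.4.2), and "participant eligibility must be determined within the 28 days prior to Day 1". Each randomised participant should therefore have two pre-dose values of each measure, normally no more than 28 days apart.

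SAP 6.5 takes as baseline the single "last available, valid, non-missing measurement taken prior to first study drug administration". That is Day 1 unless Day 1 is missing. SAP 7.1 enters this value as a covariate and adds "No additional adjustments for covariates will be made". The example code in SAP 14.2.1.10 has one baseline term: "MODEL AVAL = TRT01P|VISIT BASELINE / DDFM = KENWARDROGER". The same section leaves model details, including the covariance structure, to be settled on model fit, but mentions no second pre-dose value. SAP section 10 uses Screening mRSS only to describe the sample.

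The prose of SAP 14.2.1.10 and Protocol 12.4.4.1 names change from baseline as the response, while the code models AVAL. This matters for the choice of remedy.

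**The concern.** mRSS is a palpation score summed over 17 sites, and spirometry varies between sessions. A single reading of either is a noisy measure of the participant's pre-treatment level. A noisy covariate explains less of the outcome, and what it fails to explain stays in the residual. A second reading can recover part of that without a further visit or participant.

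Short-term efficacy against placebo is a stated secondary objective, and SAP 14.2.1.10 reports treatment differences with 95% confidence intervals and p-values. At stake is the width of those intervals for mRSS and FVC % predicted. SHAQ-DI and the two global assessments are first recorded on Day 1, so the point does not apply to them.

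**Working it through.** **Inputs from the documents.** About 30 participants, 10 per arm (SAP 3.1); gap of up to 28 days (Protocol 6.2); Screening limits as above; two-sided 5% (SAP 6.1). There is no formal sample size calculation (Protocol 12.1) and no SD or correlation, so there is no planned figure to reproduce.

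**Assumed.** Between-participant SD b, measurement-error SD e, and SD c of true change over 12 weeks:
- mRSS: b 6–7, e 2–3, c 2–5.
- FVC % predicted: b 16, e 3–4, c 2–4.
- True drift over a gap of g days has variance d = c²·g/84, that is, the same rate of change as during the 84 treatment days.

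**Step 1: simplest case.** If Screening, Day 1 and Week 12 are equally correlated (r), the residual variance is 1 − r² with one baseline and 1 − 2r²/(1+r) with both. The ratio is (1+2r)/(1+r)².

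| r | variance ratio | SE ratio |
|---|---|---|
| 0.5 | 2.0/2.25 = 0.889 | 0.943 |
| 0.7 | 2.4/2.89 = 0.830 | 0.911 |
| 0.8 | 2.6/3.24 = 0.802 | 0.896 |
| 0.9 | 2.8/3.61 = 0.776 | 0.881 |

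**Step 2: price of a second covariate.** Residual degrees of freedom fall from 26 to 25, and one more covariate can be imbalanced by chance. The interval is multiplied by (2.0595/2.0555) × √[(1+2/24)/(1+1/25)] = 1.0020 × 1.0206 = 1.023. That is about 2% wider if Screening adds nothing.

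**Step 3: allow drift.** With S Screening, B Day 1 and Y Week 12: Var S = b²+e²; Var B = b²+d+e²; Cov(S,B) = Cov(S,Y) = b²; Cov(B,Y) = b²+d; Var Y = b²+d+c²+e². The results below ignore the eligibility limits. Results for both values come from the two-covariate regression and include the factor 1.023.

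- FVC, favourable (b 16, e 4, c 2, g 0). Day 1 only: 276 − 256²/272 = 35.06. Mean: 276 − 256²/264 = 27.76, and the same for both values. Width ratios: mean √(27.76/35.06) = 0.890; both 0.890 × 1.023 = 0.910.
- FVC, unfavourable (b 16, e 3, c 4, g 28; d = 16·28/84 = 5.33). Day 1 only: 286.33 − 261.33²/270.33 = 33.70. Both: 30.48. Mean: 30.80. Width ratios: both √(30.48/33.70) × 1.023 = 0.973; mean 0.956.
- mRSS, favourable (b 6, e 3, c 2, g 0). Day 1 only: 49 − 36²/45 = 20.20. Mean or both: 49 − 36²/40.5 = 17.00. Width ratios: mean 0.917; both 0.938.
- mRSS, unfavourable (b 6, e 2, c 5, g 28; d = 25·28/84 = 8.33). Day 1 only: 73.33 − 44.33²/48.33 = 32.67. Both: 32.00. Mean: 33.08. Width ratios: both √(32.00/32.67) × 1.023 = 1.012; mean 1.006.

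**Step 4: impose the eligibility limits.** Simulated Week 12 ANCOVA, 3 × 10 participants, over the same assumed SDs and gaps of 0 to 28 days. Change in 95% interval width against Day 1 only:

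| Endpoint | Screening as second covariate | Mean of the two as sole covariate |
|---|---|---|
| FVC % predicted | −9% to −3% | −11% to −4% |
| mRSS | −5% to +1% | −7% to +1% |

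The limits on Screening mRSS trim the favourable end.

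**Step 5: which response.** Change is AVAL − BASELINE. If BASELINE is in the model, switching the response to change lowers its coefficient by 1 and alters nothing else, so the treatment difference and interval are identical. If the two-visit mean replaces BASELINE, this no longer holds. With change from Day 1 as response, the residual variance in the simplest case is 2(1−r) − (1−r)²/[2(1+r)]. At r = 0.8 that is 0.389 against 0.360 for the planned model, a ratio of 1.08. In simulation the interval was 0.4% to 4% wider than planned.

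**The case against.** The plan contains no error here. Taking the last pre-dose value as baseline is pre-specified, is consistent between protocol and SAP, and is already adjusted for. The comparisons are exploratory, are to be run only if the data show a trend and the model assumptions hold, and carry no power claim. All of that stands, and it limits the point to an optional gain.

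A reader might infer that precision is certainly being lost on both endpoints, with the mRSS interval sure to shrink by several per cent. The documents do not support that. They give no SDs, and they allow up to 28 days between the readings. The methotrexate exclusion covers only the 2 weeks before Day 1 (Protocol 5.4.3), so some Screening scores may be taken on methotrexate. If true change in that gap is large relative to rating error, Screening says little that Day 1 does not. In one limit case (correlations of 0.80 for Day 1 with Week 12, 0.90 for Screening with Day 1, 0.72 for Screening with Week 12), a second covariate leaves the residual variance unchanged and the simple mean raises it by 9%.

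A reader might also infer that averaging the two readings is the safer remedy because it costs no degree of freedom. It gives equal weight to a Screening score that was selected on eligibility, and it loses precision if the SAP's prose response is followed.

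**Conclusion.** The point holds as a minor one. The plan leaves usable pre-treatment information out of the model and bars its use. For FVC % predicted the gain survives every scenario examined: an interval 3% to 9% narrower with Screening as a second covariate, equivalent to about 6% to 21% more participants (1/0.97² = 1.06; 1/0.91² = 1.21). For mRSS the range runs from 5% narrower to 1% wider, so a gain is plausible but not established. These figures rest on assumed SDs and on drift between visits at the same rate as during treatment. They describe a Week 12 ANCOVA rather than the full repeated-measures model. Nothing here touches the primary PK objective or calls the validity of the planned estimates into question.

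**What to change.** Before unblinding, amend SAP 7.1 and 14.2.1.10, for FVC % predicted and mRSS only, to keep BASELINE as defined in SAP 6.5 and add the Screening value as a second covariate. In the code this is one extra term on the MODEL line. State which Screening value counts when an assessment was repeated or the participant was re-screened (Protocol 6.2.1). If Day 1 is missing, BASELINE already falls back on an earlier pre-dose value, so no participant drops out of the model.

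If the two-visit mean is preferred, the SAP text must say that the response is AVAL and not change from Day 1.

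Keep Day 1 as Baseline for descriptive change, CRISS and the mRSS progression criterion. The other three modelled endpoints stay as planned.

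The cost is one degree of freedom, a sentence in each of the two sections and one derived variable, with no new data. The downside is possibly no gain for mRSS, and an interval about 2% wider if Screening carries no information beyond Day 1.
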